5. GENERAL METHODOLOGY AND CONVENTIONS

The planned statistical analyses will be carried out when all safety and immunogenicity data for all participants are available and released.

5.1. Hypotheses and Decision Rules

No hypothesis testing will be performed and no formal statistical decision rules apply in this study. A descriptive estimation approach will be used to assess all safety and immunogenicity objectives.

5.2. General Methods

Time points for local reactions and systemic events refer to data within 7 days after each dose.

CIs for all endpoints in the statistical analysis will be presented as 2-sided at the 95% level.

5.2.1. Analyses for Binary Endpoints

Descriptive statistics for categorical variables (eg, proportions) are the percentage (%), the numerator (n) and the denominator (N) used in the percentage calculation, and the 95% CI where applicable.

The exact 95% CI for binary endpoints for each group will be computed using the F distribution (Clopper-Pearson).¹

[figure not shown]
The 3-tier approach will be used to summarize AEs. For both Tier 1 (if any are identified during the study) and Tier 2 events, a 95% CI for the between-group difference in proportions will be calculated based on the Miettinen and Nurminen method.² In addition, for Tier 1 events (if any), the asymptotic p-values will also be presented for the difference in proportions, based on the same test statistic and under the assumption that the test statistic is asymptotically normally distributed. For Tier 3 events, counts and percentages for each vaccine group will be provided.

5.2.2. Analyses for Continuous Endpoints

Unless otherwise stated, descriptive statistics for continuous variables are n, mean, median, standard deviation, minimum, and maximum.

5.2.2.1. Geometric Means

For immunogenicity results of serotype-specific IgG concentrations and OPA titers, the geometric means will be computed along with associated 95% CIs. The GM and associated 2-sided 95% CI will be calculated as the mean of the assay results on the natural logarithmic scale based on the t distribution, and then exponentiating the results.

5.3. Methods to Manage Missing Data

A partial AE start date (missing day or missing both month and day) will be imputed by assigning the earliest possible start date using all available information, such as the stop date of the AE and the vaccination date(s) from the same participant, following the Pfizer standard of handling incomplete AE start date. A complete missing start date for an AE is not allowed in the data collection.

The LLOQ for each assay will be provided by Vaccines Research and Development as part of the electronic data transfer or within the Clinical Testing Completion Memo prior to statistical analysis. Assay results above the LLOQ will be reported, and values below the LLOQ, denoted as BLQ, will be imputed as $0.5 \times \text{LLOQ}$ for analysis.

[figure not shown]
No additional imputation will be applied to other missing data.

[figure not shown]
6. ANALYSES AND SUMMARIES

- **6.1. Primary Endpoints**
- **6.1.1. Primary Safety Endpoints**
- 6.1.1.1. Local Reactions

6.1.1.1.1. Main Analysis

- Estimand: Proportions of participants reporting prompted local reactions (redness, swelling, and pain at the injection site) within 7 days after the last assigned vaccination.
- Analysis set: Safety population (Section 4).
- Analysis time point: Within 7 days after the last assigned vaccination.
- Analysis methodology: Descriptive statistics.
- Reporting results: Proportions of participants reporting prompted local reactions will be summarized by maximum severity level. The percentage (%), the numerator (n), and the denominator (N) used in the percentage calculation, and the corresponding 95% Clopper-Pearson CI will be presented for each vaccination group.

6.1.1.2. Systemic Events

6.1.1.2.1. Main Analysis

- Estimand: Proportions of participants reporting prompted systemic events (fever, decreased appetite, irritability, and drowsiness/increased sleep) within 7 days after the last assigned vaccination.
- Analysis set: Safety population (Section 4).
- Analysis time point: Within 7 days after the last assigned vaccination.
- Analysis methodology: Descriptive statistics.
- Reporting results: The percentage (%), the numerator (n), and the denominator (N) used in the percentage calculation, and the corresponding 95% Clopper-Pearson CI will be presented for each vaccination group.

6.1.1.3. Adverse Events

6.1.1.3.1. Main Analysis

- Estimand: Proportions of participants reporting AEs.
- Analysis set: Safety population (Section 4).
- Analysis time point: Vaccination to 1 month after the last assigned vaccination (in the 2-dose group this will be the last vaccination to 1 month after the last assigned vaccination for reporting).
- Analysis methodology: Descriptive statistics.
- Reporting results: For all 3 tiers, the numerator (n) and the denominator (N) used in the percentage calculation, the percentage (%), and the corresponding 2-sided 95% CI for participants reporting any AE, each SOC, and each PT within each SOC will be presented by vaccine group.

In addition, for AEs classified as Tier 2 events, the differences in percentages and associated 2-sided 95% CIs for between-group comparisons (20vPnC - 13vPnC control) will be provided for each of the 20vPnC vaccine groups (the comparison will be the percentage from the last vaccination to 1 month after the last vaccination in the 2-dose group).

Further, for Tier 1 events, if any are identified, the difference in percentages, the associated 2-sided 95% CI for the risk difference, and the asymptotic p-values will also be provided.

6.1.1.4. Serious Adverse Events

6.1.1.4.1. Main Analysis

- Estimand: Proportions of participants reporting SAEs.
- Analysis set: Safety population (Section 4).
- Analysis time point: Vaccination to 1 month after the last assigned vaccination (the last vaccination to 1 month after the last vaccination in the 2-dose group).
- Analysis methodology: Descriptive statistics.
- Reporting results: The numerator (n), and the denominator (N) used in the percentage calculation, the percentage (%), and corresponding 2-sided 95% CI will be presented for each vaccination group.

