9.3.4. Primary Endpoint(s)/Estimand(s) Analysis

Objective	Estimands	Statistical Analysis Methods
Safety	
 Proportions of participants with local reactions (redness, swelling, and pain at the injection site) within 7 days after the last assigned vaccination from each group Proportions of participants with systemic events (fever, decreased appetite, irritability, and drowsiness/increased sleep) within 7 days after the last assigned vaccination from each group 	
 Descriptive summary statistics for participants with each local reaction/systemic event within 7 days after each dose by maximum severity and cumulatively across severity levels
	
 AEs from vaccination to 1 month after the last assigned vaccination in each group 	
 Three-tier approach
	
 SAEs from vaccination to 1 month after the last assigned vaccination in each group 	
 Descriptive summary statistics

Objective	Estimands	Statistical Analysis Methods
Immunogenicity	
 Percentage of participants with IgG concentrations to the 7 additional serotypes with a predefined level^a 1 month after the last assigned vaccination in each group 	
 Descriptive summary statistics •

a. The predefined level is 0.35 µg/mL for all 7 additional serotypes.

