3. ENDPOINTS AND BASELINE VARIABLES: DEFINITIONS AND CONVENTIONS

3.1. Primary Endpoints

3.1.1. Primary Safety Endpoints

- Prompted local reactions (redness, swelling, and pain at the injection site) within 7 days after the last assigned vaccination.
- Prompted systemic events (fever, decreased appetite, drowsiness/increased sleep, and irritability) within 7 days after the last assigned vaccination.
- AEs from vaccination to 1 month after the last assigned vaccination.
- SAEs from vaccination to 1 month after the last assigned vaccination.

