3.1.1.4. Adverse Events

AEs will be categorized according to MedDRA terms. AEs will be assessed from the time of informed consent through 1 month after the last assigned vaccination.

The primary endpoint "AEs from vaccination through 1 month after the last assigned vaccination" and other supportive AE endpoints will be summarized by SOC and PT on a participant level.

This primary endpoint will be supported by summaries and listings of related AEs, severe AEs, and immediate AEs (within the first 30 minutes after each dose).

AE reporting will be based on the specific reporting period. Missing AE start dates will be imputed following the Pfizer data standard rules as described in Section 5.3.

A 3-tier approach will be used to summarize AEs from vaccination through 1 month after the last assigned vaccination. Under this approach, AEs are classified into 1 of 3 tiers. Different analyses will be performed for different tiers (see Section 6.1.1.3.1). The control group for both the 1-dose and 2-dose 20vPnC groups (after the last assigned dose) is the 13vPnC group.

- Tier 1 events: These are prespecified events of clinical importance and are identified in a list in the product's Safety Review Plan. No Tier 1 events have been identified to date for 20vPnC.
- Tier 2 events: These are events that are not Tier 1, but are "common." A MedDRA PT is defined as a Tier 2 event if there are at least 4 participants with the AE term in at least 1 vaccine group.
- Tier 3 events: These are events that are neither Tier 1 nor Tier 2.

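### The primary AE/SAE endpoint is defined from vaccination, but the 2-dose arm is counted only from Dose 2, so events between doses enter no visible main percentage

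*SAP*

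**What the plan says.** In the 2-dose arm, Dose 2 is given 56 to 70 days after Dose 1, and the follow-up visit comes 28 to 42 days after that (Protocol 4.1). The last assigned vaccination in this arm is Dose 2 (Protocol 4.1, SAP 2.3). AEs and SAEs are collected from consent onward, including at Visit 2 for the time since Dose 1 (Protocol 8.9.1.2, SAP 2.3).

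**Wide window, from vaccination.** Protocol 9.3.4 lists "SAEs from vaccination to 1 month after the last assigned vaccination in each group", with a parallel line for AEs. SAP 3.1.1 repeats it: "SAEs from vaccination to 1 month after the last assigned vaccination". SAP 3.1.1.4 carries it into the tier rule: "A 3-tier approach will be used to summarize AEs from vaccination through 1 month after the last assigned vaccination". The same section adds "A MedDRA PT is defined as a Tier 2 event if there are at least 4 participants with the AE term" in at least one vaccine group.

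**Narrow window, after the last assigned vaccination.** This is the wording of the estimands (Protocol 1.1 and 3, SAP 2.2), the synopsis statistical methods and the safety paragraph of Protocol 9.5. SAP 6.1.1.3.1 narrows the AE analysis explicitly: "in the 2-dose group this will be the last vaccination to 1 month after the last assigned vaccination for reporting". For Tier 2 differences it says "the comparison will be the percentage from the last vaccination to 1 month after the last vaccination in the 2-dose group". SAP 6.1.1.4.1 does the same for SAEs: "Vaccination to 1 month after the last assigned vaccination (the last vaccination to 1 month after the last vaccination in the 2-dose group".

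**Prompted events.** The methods column of Protocol 9.3.4 calls for "Descriptive summary statistics for participants with each local reaction/systemic event within 7 days after each dose by maximum severity". SAP 5.2, and the sentence in SAP 3.1.1.1 that introduces maximum severity, also refer to each dose. The formula that follows in SAP 3.1.1.1, and the main analyses in SAP 6.1.1.1.1 and 6.1.1.2.1, cover only the last assigned vaccination.

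**The concern.** One primary endpoint has two windows, and in the 2-dose arm they give different counts. The general phrase is not merely a loose name for the narrow window: the SAP needed a parenthesis to restrict it for this arm, which means that without the parenthesis it starts at Dose 1.

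Describing the safety of 20vPnC is a primary objective, and the 2-dose schedule is one of the two 20vPnC regimens studied. A reader of Protocol 9.3.4 would take the 2-dose percentages to cover the whole regimen. Programmed from SAP 6.1.1, they cover the month after Dose 2. For a child who goes on to Dose 2, an SAE between doses would be collected and reported to the sponsor, yet absent from the main SAE percentage. SAP 6.5.4 makes the mismatch visible. It summarises medications used to treat SAEs from the time of vaccination, so a medication could be tabulated while the SAE it treated is missing from the main SAE row.

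**Working it through.** **Inputs.** Interval between doses g = 56 to 70 days and follow-up f = 28 to 42 days (Protocol 4.1). N = 120 per group (Protocol 9.5). Two-sided 95% Clopper-Pearson intervals (SAP 5.2 and 5.2.1). No event rate is assumed.

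**1. The plan's own safety figure.** Table 5 gives the probability of at least one event, 1 − (1 − p)^120. For p = 1%, 2% and 5% this is 70.1%, 91.1% and 99.8%, as printed. The table is correct and is not in dispute.

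**2. Share of scheduled time after Dose 1 that lies before Dose 2**, g/(g + f):

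| g | f | g + f | share |
|---|---|---|---|
| 56 | 42 | 98 | 57.1% |
| 70 | 42 | 112 | 62.5% |
| 56 | 28 | 84 | 66.7% |
| 70 | 28 | 98 | 71.4% |

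**3. What the 1-dose 20vPnC arm covers.** Its main row describes the first 28 to 42 days after a first dose. That leaves between 56 − 42 = 14 and 70 − 28 = 42 days before Dose 2 with no counterpart in any arm's main row.

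**4. One child whose only SAE falls between doses, and who receives Dose 2.**
- Protocol 9.3.4 and SAP 3.1.1: 1/120 = 0.8%. Lower limit 1 − 0.975^(1/120) = 0.02%; upper limit, the 97.5% quantile of Beta(2, 119), = 4.6%.
- SAP 6.1.1.4.1: 0/120 = 0%. Upper limit 1 − 0.025^(1/120) = 3.0%.

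**5. Prompted events side by side.**

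| Place | Period |
|---|---|
| Protocol 9.3.4, methods column | each dose |
| SAP 5.2 | each dose |
| SAP 3.1.1.1, sentence before the formula | each dose |
| SAP 3.1.1.1, formula | last assigned vaccination |
| SAP 6.1.1.1.1 and 6.1.1.2.1 | last assigned vaccination |

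The intent to report per dose is stated three times. The formula and the main analyses do not carry it out for Dose 1 of the 2-dose arm.

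**The case against.** The strongest reply is that the operative window is already settled. The estimands, the synopsis, Protocol 9.5 and both SAP main analyses agree on it, and the SAP is the document that gives the detailed method. The window also gives every arm about one month of observation, which makes the difference from 13vPnC interpretable. All of this stands, and it is why the narrow window should stay. It does not remove the conflict with the endpoint definitions, nor does it place between-dose events in a visible main row.

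Other parts of the reply also stand, and they limit what may be inferred:
- **Lost or hidden data.** A reader might infer that between-dose safety data are lost. They are collected, SAEs go to the sponsor within 24 hours (Protocol 8.3.1.1), and a data monitoring committee reviews safety (Protocol 10.1.5.1).
- **No between-dose table at all.** The public SAP does not support this. Its numbering skips sections (3.1.1.3, 3.3, 6.3 and 6.4), and SAP 3.1.1.4 mentions supportive summaries of related, severe and immediate AEs. Only the immediate AEs are tied to each dose, and no window is given for the rest.
- **An undecidable tier rule.** SAP 3.1.1.4 states the rule over the wide window, but SAP 6.1.1.3.1 sets the post-Dose-2 window for all three tiers. Counting the cut-off in that window is the natural reading, so one clarifying sentence is enough.
- **Children who stop after Dose 1.** The estimand heading requires safety follow-up after the assigned vaccination and applies to AEs and SAEs as well as diary events, so it points to leaving these children out of post-Dose-2 rows. What stays loose is the mix of last and last assigned vaccination in SAP 6.1.1.3.1 and 6.1.1.4.1, and the grouping by vaccine as administered in SAP 4. Their number cannot be read off the gap between 120 enrolled and 105 evaluable: 105 is a planning target, and a child can be non-evaluable for many other reasons.

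**Conclusion.** The inconsistency is real and worth correcting before the tables are programmed. As written, AEs and SAEs in the 56 to 70 days between doses fall inside the primary endpoint as defined and outside every visible main percentage for children who receive Dose 2. The excluded share is 57% to 71% of scheduled time after Dose 1. It should not be read as a share of events, since the documents give no event rates by period. The one-child case (0.8% against 0%) shows that the two definitions can disagree; it does not predict that they will.

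A reader might conclude that the post-Dose-2 window is itself wrong. It is not: it matches the estimands and is the right basis for the comparison with 13vPnC. The study is descriptive, with no hypothesis test (Protocol 9.1.1, SAP 5.1), so no error rate, power or sample size changes. The conclusion concerns the visible text only, and the request for extra rows lapses if a supportive table already provides them.

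**What to change.** 1. Align Protocol 9.3.4 and SAP 3.1.1 and 3.1.1.4 with SAP 6.1.1.3.1 and 6.1.1.4.1. Keep the post-last-dose window for the comparison with 13vPnC, and state that the Tier 2 count of 4 participants uses that same window.
2. Unless an existing supportive table already does so, add descriptive AE and SAE rows for the 2-dose arm: (a) from Dose 1 to before Dose 2, and (b) from Dose 1 to 1 month after Dose 2. Label both with exposure time and as not comparable with the 1-dose arms.
3. Apply the maximum-severity formula in SAP 3.1.1.1 and the analyses in SAP 6.1.1.1.1 and 6.1.1.2.1 per dose.
4. State that post-Dose-2 rows use children who received Dose 2 as the denominator, and that events in children who received only Dose 1 appear in the Dose 1 and whole-regimen rows of the 2-dose group.

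The cost is a few extra tables from data already collected; SAP 6.5.2.1 already tabulates the number receiving each dose. Protocol 9 and SAP 2 require a protocol amendment for major modifications of the primary endpoint definition or its analysis. Because the operative window stays, the protocol change is an alignment of wording. The downside is a whole-regimen row covering 84 to 112 days next to 1-dose rows covering 28 to 42 days, which would mislead if the label were dropped.

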6.1.2. Primary Immunogenicity Endpoints

6.1.2.1. Participants With Predefined Pneumococcal Serotype-Specific IgG Concentrations at 1 Month After the Last Assigned Vaccination for the 7 Additional Serotypes

- Estimand: For each of the 7 additional serotypes in 20vPnC, the percentages of participants with predefined serotype-specific IgG concentrations.
- Analysis set: Evaluable immunogenicity population (Section 4).
- Analysis time point: 1 Month after the last assigned vaccination.
- Analysis methodology: Descriptive statistics.
- Reporting results: For each of the 7 additional serotypes, the numerator (n) and the denominator (N) used in the percentage calculation, the percentage (%), and the corresponding 2-sided 95% CI for participants with predefined IgG concentrations from each vaccine group.

Figures:

Percentages (and corresponding 95% CIs) of participants achieving predefined serotype-specific IgG concentrations 1 month after the last dose will be presented in a vertical bar chart.

6.2. Secondary Endpoints

6.2.1. IgG Concentration

6.2.1.1. Pneumococcal Serotype-Specific IgG Concentrations

- Estimand: Pneumococcal serotype-specific IgG concentrations 1 month after the last assigned vaccination.
- Analysis set: Evaluable immunogenicity population (Section 4).
- Analysis time point: 1 Month after the last assigned vaccination.
- Analysis methodology: Descriptive statistics.

• Reporting results: IgG GMCs with their associated 95% CIs will be summarized at 1 month after the last assigned vaccination for each 20vPnC serotype by each vaccination group.

6.2.1.2. Participants With Predefined Pneumococcal Serotype-Specific IgG Concentrations at 1 Month After the Last Assigned Vaccination for the 13 Matched Serotypes

- Estimand: For each of the 13 matched serotypes in 20vPnC, the percentages of participants with predefined serotype-specific IgG concentrations.
- Analysis set: Evaluable immunogenicity population (Section 4).
- Analysis time point: 1 Month after the last assigned vaccination.
- Analysis methodology: Descriptive statistics.
- Reporting results: For each of the 13 matched serotypes, the numerator (n) and the denominator (N) used in the percentage calculation, the percentage (%), and the corresponding 2-sided 95% CI for participants with predefined IgG concentrations from each vaccine group.

[figure not shown]
Figures:

Percentages (and corresponding 95% CIs) of participants achieving predefined serotype-specific IgG concentrations 1 month after the last dose will be presented in a vertical bar chart.

6.2.2. OPA Titers

- Estimand: Pneumococcal serotype-specific OPA titers 1 month after the last dose.
- Analysis set: Evaluable immunogenicity population (Section 4).
- Analysis time point: 1 Month after the last assigned vaccination.
- Analysis methodology: Descriptive statistics.
- Reporting results: OPA GMTs with their associated 95% CIs will be summarized separately before and 1 month after vaccination for each 20vPnC serotype by each vaccination group.

6.5. Baseline and Other Summaries and Analyses

6.5.1. Baseline Summaries

6.5.1.1. Demographic Characteristics

Demographic characteristics, including age at vaccination, sex, race, and ethnicity, will be summarized for the safety population and the evaluable immunogenicity population by vaccination group.

6.5.1.2. Medical History

Each reported medical history term will be mapped to an SOC and PT according to MedDRA. The number and percentage of participants with an assigned vaccine having at least 1 diagnosis, overall and at each SOC and PT level, will be summarized by vaccination group for the safety population.

6.5.2. Study Conduct and Participant Disposition

6.5.2.1. Participant Disposition

The number and percentage of randomized participants will be included in the participant disposition summary. In addition, the numbers and percentages of participants who receive each vaccination (Dose 1 or 2), who completed the follow-up visits (1 month after the last assigned vaccination), who completed all visits, and who withdrew, along with the reasons for withdrawal, will be tabulated by vaccine group (according to randomized group assignment). The reasons for withdrawal will be those as specified in the database.

Randomized participants excluded from the safety or immunogenicity analysis populations will also be summarized separately, along with the reasons for exclusion, by vaccine group.

6.5.2.2. Blood Samples for Assay

The number and percentage of enrolled participants providing blood samples within and outside of protocol-specified time frames will be tabulated.

6.5.3. Investigational Vaccine

6.5.3.1. Vaccination Timing and Administration

The number and percentage of participants enrolled and receiving vaccine (2-dose group only) within the protocol-specified time frame, as well as before and after the specified time frame, will be tabulated for the 2-dose group. The denominator for the percentages is the total number of participants in the given vaccination group.

6.5.4. Concomitant Vaccines, Medications, and Nondrug Treatments

Each prior/concomitant vaccine will be summarized according to the ATC fourth-level classification. The number and percentage of enrolled participants receiving concomitant vaccines will be summarized according to vaccination group.

Concomitant medications used to treat SAEs will be summarized from the time of vaccination to 1 month after the last vaccination (safety population).

Participants' time since each previous dose of 13vPnC will be summarized descriptively.

